***Nephrotoxicity (Specific Renal Criterion)***

Patients who meet renal toxicity criteria will be diagnosed/followed up and captured eCRF will be reported in listing as well as summarized.

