8.6.3 Clinical laboratory evaluations

Due to the emergency setting of the patient, screening/baseline laboratory evaluation can be performed locally. A central laboratory will be used for all other time points for the analysis of all specimens collected. Timings of blood sample collection are outlined in the [Table 8-1](#). Details on the collections, shipment of samples and reporting of results by the central laboratory are provided to investigators in the laboratory manual. Abnormal laboratory parameters, inconsistent with clinical presentation of stroke or which cause suspicion of an underlying medical condition, should be repeated for confirmation. Additional local lab samples will be taken according to the site's local practice to adhere to local standard of care for ICH patients.

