8.6.3.2 Clinical chemistry

Blood samples will be collected at the scheduled visits indicated in [Table 8-1](#) and the parameters assessed will include: electrolytes (Na, K, Cl, bicarbonate, Ca, Mg, P), non-fasting glucose, albumin, alkaline phosphatase, creatinine, ALT, AST, GGT, amylase, total bilirubin, conjugated bilirubin, and CRP. After the initial screening chemistry, total cholesterol, triglycerides, HDL, and LDL may or may not be repeated at the discretion of the Investigator.

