Autoimmune hepatitis	
• ANA & ASMA titers, total IgM, IgG, IgE, IgA
Alcoholic hepatitis	
• Ethanol history, GGT, MCV, CD-transferrin
Nonalcoholic steatohepatitis	
• Ultrasound or MRI
Hypoxic/ischemic hepatopathy	
• Medical history: acute or chronic CHF, hypotension, hypoxia, hepatic venous occlusion. Ultrasound or MRI.
Biliary tract disease	
• Ultrasound or MRI, ERCP as appropriate.
Wilson disease	
• Ceruloplasmin
Hemochromatosis	
• Ferritin, transferrin
Alpha-1-antitrypsin deficiency	
• Alpha-1-antitrypsin

16 Appendix 2: Specific Renal Alert Criteria and Actions

Table 16-1 Specific Renal Alert Criteria and Actions

Criteria	Action required
Serum creatinine (sCr) increase 25 – 49% compared to baseline	
 Consider causes and possible interventions Follow up within 2-5 days
Serum creatinine increase > 50%	
 Consider causes and possible interventions Repeat assessment within 24-48h if possible Consider drug interruption or discontinuation unless other causes are diagnosed and corrected Consider hospitalization and specialized treatment
Protein-creatinine or albumin-creatinine ratio increase \geq 2-fold or new onset dipstick proteinuria \geq 1+ or Albumin-creatinine ratio (ACR) \geq 30 mg/g or \geq 3 mg/mmol; or Protein-creatinine ratio (PCR) \geq 150 mg/g or >15 mg/mmol	
 Consider causes and possible interventions Assess serum albumin & serum protein Repeat assessment to confirm Consider drug interruption or discontinuation unless other causes are diagnosed and corrected
New onset glucosuria on urine dipstick (unless related to concomitant treatment, diabetes)	
Assess & document:
 
 Blood glucose (fasting) Serum creatinine Urine albumin-creatinine ratio
New hematuria on dipstick	
Assess & document:
 
 Urine sediment microscopy Assess sCr and urine albumin-creatinine ratio Exclude infection, trauma, bleeding from the distal urinary tract/bladder, menstruation Consider bleeding disorder

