### **Clinical laboratory evaluations**

Due to the emergency setting of the patient, screening/baseline laboratory evaluation can be performed by locally. A central laboratory will be used for all other timepoints for the analysis of all specimens collected.

Laboratory data from all sources (central and local laboratories) will be combined. All laboratory values will be converted into International System (SI) units.

Raw values as well as absolute and relative change from baseline values for hematology, biochemistry and urinalysis (quantitative and qualitative) laboratory parameters will be summarized descriptively per time point and treatment arm.

Urinalysis parameters will be listed.

Change from baseline will only be summarized for patients with both baseline and post baseline values and will be calculated as:

$$\text{change from baseline} = \text{post baseline values} - \text{baseline value}$$

Shift tables based on normal ranges to compare baseline to the worst post-baseline value will be provided by parameter and treatment arm for hematology, biochemistry and urinary laboratory data.

A listing of all laboratory values with values flagged to show the corresponding range classifications (High, Low) relative to the laboratory reference ranges will be provided by laboratory category and treatment arm.

Normal ranges by laboratory parameter will be provided in a separate listing.

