***Liver event definition:***

The liver event criteria [Table 8-2](#) will be evaluated using clinical chemistry parameters.

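### The renal toxicity summary rests on eCRF capture, so the number of patients meeting the creatinine criteria depends on sites recognising rises that may stay within the normal range

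*SAP*

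**What the plan says.** **Renal, SAP section 8.2 (Nephrotoxicity).** The whole text is one sentence: "Patients who meet renal toxicity criteria will be diagnosed/followed up and captured eCRF will be reported in listing as well as summarized". It gives no threshold, no derivation rule, no denominator and no reference to the protocol appendix that holds the criteria.

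**Renal, protocol Appendix 2, Table 16-1.** The first creatinine criterion is "Serum creatinine (sCr) increase 25 – 49% compared to baseline". The second is "Serum creatinine increase > 50" per cent. Neither refers to the laboratory's normal range. The table also has urine criteria (proteinuria, glucosuria, haematuria).

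**Liver, SAP section 8.2 (Liver event definition).** The criteria are tabulated and "will be evaluated using clinical chemistry parameters".

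**Available data.** The scheduled chemistry panel in protocol section 8.6.3.2 includes creatinine ("albumin, alkaline phosphatase, creatinine, ALT, AST, GGT, amylase, total bilirubin, conjugated bilirubin, and CRP"). Under protocol section 8.6.3, "screening/baseline laboratory evaluation can be performed locally"; afterwards, in the SAP's words, "A central laboratory will be used for all other timepoints for the analysis of all specimens collected". The SAP combines central and local results and converts them to SI units.

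**Planned laboratory outputs, SAP section 8.2.** These are "Shift tables based on normal ranges to compare baseline to the worst post-baseline value", a listing flagged High or Low against reference ranges, and descriptive statistics of absolute and relative change by time point and arm.

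**The concern.** The protocol defines creatinine alerts relative to the patient, but the SAP's categorical laboratory outputs are relative to the normal range. In the visible text the only route to a number of patients meeting the renal criteria is what was captured on the eCRF. A rise that stays within range can be missing from that number if nobody at the site compares it with the baseline value, even though the database holds both results.

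Safety is a secondary objective, and with about 33 patients per arm the renal counts will be small. A few unrecorded cases could change how the two arms compare. The number would then partly reflect how closely sites checked for rises, as well as renal function.

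**Working it through.** The plan states no figure on this point, so there is none to reproduce. The check has three parts.

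**1. Which rises the range-based outputs cannot show.** Take a baseline b and a fractional rise r. The later value is b × (1 + r), which is at or below the ULN when b ≤ ULN / (1 + r).

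- r = 0.25: b ≤ ULN / 1.25 = 0.80 × ULN
- r = 0.49: b ≤ ULN / 1.49 = 0.671 × ULN
- r = 0.50: b ≤ ULN / 1.50 = 0.667 × ULN

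For example, a baseline of 0.75 × ULN that rises 25% reaches 0.9375 × ULN. It is Normal-to-Normal in the shift table and carries no flag in the listing. This is algebra, with two simplifications: the same ULN applies at baseline and follow-up, and the second row of Table 16-1, which does not repeat the reference to baseline, is read like the first.

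**2. Whether another planned output supplies the count.**

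- Shift table and High/Low flag: no, for baselines in the window above.
- Relative change by time point: it gives distribution statistics, not the number of patients who cross 25% or 50% at any time. Under SAP section 4.4, descriptive summaries generally leave out unscheduled and repeat values.
- Adverse event tables: only in part. Under protocol section 9.1 a laboratory abnormality is an adverse event only if it causes signs or symptoms, is clinically significant or needs therapy.
- Renal listing and summary: yes, to the extent that the eCRF holds the event.

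**3. What incomplete capture would do.** The documents give neither the true alert rate p nor the share s that sites capture, so both are assumptions here. With n = 33 per arm (SAP section 1.4), the expected recorded count is n × p × s. The chance that at least one patient in an arm is missed is 1 − (1 − p(1 − s))^33.

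| p | True expected count | s | Recorded expected count | Chance of ≥ 1 missed |
|---|---|---|---|---|
| 10% | 3.3 | 75% | 2.5 | 0.57 |
| 10% | 3.3 | 50% | 1.7 | 0.82 |
| 20% | 6.6 | 75% | 5.0 | 0.82 |
| 20% | 6.6 | 50% | 3.3 | 0.97 |
| 30% | 9.9 | 75% | 7.4 | 0.92 |
| 30% | 9.9 | 50% | 5.0 | 0.995 |

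With full capture (s = 100%) nothing is missed. The table shows how sensitive the count would be; it does not predict an under-count.

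**The case against.** Four points can be made for the plan.

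**The SAP does not exclude derivation.** The renal sentence is garbled, SAP section 1.1 leaves programming specifications to separate documents, and protocol Table 16-2 allows renal data to arrive by electronic data load as well as through the CRF. This stands: the absence of a derivation is inferred from the sentence's silence and the contrast with the liver text. It is still a reason to write the rule down.

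**Sites have a duty to act.** Protocol section 9.4 requires follow-up of every renal laboratory trigger and recording in the CRF as appropriate. How the central laboratory reports to sites is in a manual not seen here, so a percentage-rise alert is neither described nor ruled out. A reader might infer that sites will miss within-range rises; the documents do not support that. They show only that the count depends on recognition.

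**The rises are not hidden.** A reader might also infer that a low eCRF count would pass for renal safety. That goes too far. Relative change is summarised by arm and visit, and the default statistics in SAP section 4.2 include the upper quartile and maximum, so the largest scheduled rise would be printed even if within range. Boxplots (SAP section 8.3) and a listing of all values are also planned.

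**The liver contrast is limited.** For liver events the SAP promises profile graphs and a listing, not a by-arm count. The contrast concerns how cases are identified, not how they are tabulated.

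It is also tempting to size the problem from an assumed creatinine distribution. With a ULN of 1.2 mg/dL and normal-range baselines from a Normal distribution with mean 0.9 and SD 0.25, about 67% of patients could rise 25% unflagged and 39% could rise 50%. Adding a lower normal limit of 0.6 mg/dL makes these 62% and 30%. All these inputs are assumptions, and the results are shares of patients who could rise unflagged, not missed cases.

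**Conclusion.** The point holds in a limited form. As written, the renal summary draws on eCRF capture with no stated derivation, and no output in the visible text counts, from the laboratory data, the patients who meet the creatinine criteria. The blind window of the range-based outputs is exact under the simplifications stated: normal baselines at or below 0.80 × ULN for a 25% rise and 0.667 × ULN for a 50% rise.

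Only the patient-level count is exposed. By-arm presentation of that count follows from the SAP's general conventions, since the renal sentence names neither arm nor count. Whether any cases would be lost, and how many, is unknown from the documents. The safety analyses are descriptive and the primary analysis is unaffected, so this is a change to consider.

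**What to change.** Keep the eCRF renal listing and summary, including the urine criteria, and add to the SAP:

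> The creatinine criteria of protocol Table 16-1 will also be derived from the combined central and local laboratory data, using the maximum post-first-dose value (scheduled and unscheduled) relative to baseline. The number and percentage of patients meeting each criterion will be tabulated by arm on the Safety Set, among patients with a baseline and at least one post-baseline value. Derived events without an eCRF record will be flagged, and the laboratory source of the baseline will be shown.

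Before programming, the sponsor must reconcile the two creatinine bands in Table 16-1: read literally, a rise above 49% up to and including 50% belongs to neither.

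The cost is one SAP paragraph and one extra table from data already collected, with no change to visits, sampling or patient management. The downside is that some derived rises may reflect the switch from a local to the central laboratory, which is why the source of the baseline should be shown.

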***Pregnancy test and assessments of fertility***

Pregnancy testing will be done for all female patients of childbearing potential at screening/baseline and follow-up visits (Day 30 or Day 90). Listing will be produced by treatment and patients.

**Adverse events (AEs)**

All information obtained (e.g. relatedness to study drug, action taken etc.) on adverse events will be displayed by treatment and patient. AEs will be coded using the latest version of MedDRA available at the time of clinical database lock.

AEs summarized will be all events recorded during the study. Any AE with a missing start date will be considered as starting in the study.

The number and percentage of subjects with adverse events will be tabulated by body system and preferred term with a breakdown by treatment. A patient with multiple AEs within a body system is only counted once towards the total of this body system.

The following AE summaries will be produced by treatment:

- AEs, regardless of study drug relationship by primary system organ class and preferred term
- AEs, regardless of study drug relationship by primary system organ class and preferred term and severity
- AEs, regardless of study drug relationship by primary system organ class and preferred term and maximum CTCAE grade (all grades and grade 3/4 )

- AEs, with suspected study drug relationship by primary system organ class and by preferred term
- Serious adverse events (SAEs), regardless of study drug relationship, by primary system organ class and preferred term
- SAEs, with suspected study drug relationship, by primary system organ class and preferred term
- AEs leading to study drug discontinuation, regardless of study drug relationship, by primary system organ class and preferred term
- AEs requiring dose adjustment or study-drug interruption, regardless of study drug relationship, by primary system organ class and preferred term
- AEs requiring additional therapy, regardless of study drug relationship, by primary system organ class and preferred term
- Non-serious AEs (ie, AEs excluding serious AEs), regardless of study drug relationship, by primary system organ class and preferred term

Fatal AEs suspected to be related to study treatment will be provided by SOC and PT.

- Fatal SAEs regardless of study drug relationship will be provided by SOC and PT.

AEs will be summarized by presenting the number and percentage of patients having at least one AE, and having at least one AE by system organ class and/or preferred, severity and relation to study drug by treatment arm.

An overall summary of type of AEs (e.g. serious, leading to study drug discontinuation, requiring dose adjustment or/and interruption) will be presented by treatment (overall and severe). The overall summary will present the number and percentage of patients having at one AE and the occurrence of event. If for a same patient, several consecutive AEs (irrespective of study treatment causality, seriousness and severity) occurred with the same SOC and PT:

- a single occurrence will be counted if there is  $\leq 1$  day gap between the (non missing) end date of the preceding AE and the (non missing) start date of the consecutive AE.
- more than one occurrence will be counted if there is  $> 1$  day gap between the end date of the preceding AE and the start date of the consecutive AE, or if start date or end date are missing.

For occurrence, the presence of at least one SAE / SAE suspected to be related to study treatment / non SAE has to be checked in a block (e.g., among AE's in a  $\leq 1$  day gap block, if at least one SAE is occurring, then one occurrence is calculated for that SAE).

Any information collected (e.g. relation to study drug, action taken etc.) will be listed as well as the duration of the AE. If start date or end date is partially missing, it will be imputed as described in this SAP appendix, before to compute the duration of the AE.

The listings of all deaths, serious adverse events, adverse events leading to study drug discontinuation, and adverse events requiring dose adjustment or interruption will also be provided.

For the legal requirements of ClinicalTrials.gov and EudraCT, two required tables will be provided by system organ class and preferred term on the safety set population. The first one will be on non-serious treatment emergent adverse events (non-serious TEAEs) with an incidence greater than 1%. The second one will be on serious treatment emergent adverse events (serious TEAEs) or SAEs suspected to be related to study treatment. These two tables will be produced by Novartis.

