9.1 Adverse events

An adverse event (AE) is any untoward medical occurrence (i.e., any unfavorable and unintended sign [including abnormal laboratory findings], symptom or disease) in a patient after **providing written informed consent** for participation in the study until the end of study visit. Therefore, an AE may or may not be temporally or causally associated with the use of a medicinal (investigational) product.

In addition, all reports of intentional misuse and abuse of the study treatment are also considered an adverse event irrespective if a clinical event has occurred. See [Section 9.5](#) for an overview of the reporting requirements.

The occurrence of adverse events must be sought by non-directive questioning of the patient at each visit during the study. Adverse events also may be detected when they are volunteered by the patient during or between visits or through physical examination finding, laboratory test finding, or other assessments.

Abnormal laboratory values or test results constitute adverse events only if they fulfill at least one of the following criteria:

- they induce clinical signs or symptoms,
- they are considered clinically significant, or
- they require therapy.

Clinically significant abnormal laboratory values or test results should be identified through a review of values outside of normal ranges/clinically notable ranges, significant changes from baseline or the previous visit, or values which are considered to be non-typical in patients with underlying disease. Investigators have the responsibility for managing the safety of individual subject and identifying adverse events. Alert ranges for liver and kidney related events are included in [Appendix 1](#) and [Appendix 2](#), respectively.

Adverse events should be recorded on the Adverse Events CRF under the signs, symptoms or diagnosis associated with them, and accompanied by the following information:

1. CTCAE severity grade (1-5)

If CTCAE grading does not exist for an adverse event, use: 1=mild, 2=moderate, 3=severe 4=life threatening* (see [Section 9.2](#) for definition of a serious adverse event (SAE))

*Note: There may be cases where a CTCAE with a grade of 4 (life-threatening) may not necessarily be an SAE (e.g. certain laboratory abnormalities in the absence of meeting other seriousness criteria).

CTCAE grade 5 (death) is not used, but is collected as a seriousness criteria and also collected in other CRFs (e.g. Study Completion, Death/Survival).

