9.2.2 SAE reporting

IMPORTANT: To comply with regulations, all suspected, unexpected, serious adverse reactions (SUSARs) occurring in a clinical trial must be reported in an expedited timeframe (7 or 15 days) to Competent Authorities.

However, regulations do allow that certain adverse experiences that would ordinarily fall under the SAE definition can be handled differently. These exemptions from reporting of SAEs are particularly relevant to studies in high morbidity and high mortality populations where study subjects are generally sicker, such as patients with ICH, and often carry significant concomitant disease burdens.

- **Event(s) common in the patient population under study:** The unblinding of single SAEs that are relatively common in the patient population under study, for SUSAR reporting, often does not increase the understanding of safety, and can damage the integrity of the blinded nature and analysis of a study. The following SAEs commonly seen in the ICH patient population will still be captured by the investigators as SAEs in the CRF and reported to Novartis, but they will not be unblinded during the course of the study, even if considered "related" to study treatment by the reporting investigator, nor reported on an expedited basis to regulatory authorities:
 1. **Ventricular extension of hemorrhage with increased ventricular pressure requiring surgical intervention (e.g., external ventricular drainage), and**
 2. **Expansion of initial intracerebral hemorrhage requiring surgical evacuation.**

Additionally, these safety data will be reviewed in an expedited timeframe of 15 days by the external DMC.

Screen Failures

Note the following requirement for Screen Failures: SAEs occurring after the patient has provided informed consent until the time the patient is deemed a Screen Failure must be reported to Novartis.

Randomized Subjects

To ensure patient safety, every SAE, regardless of causality, occurring after the patient has provided informed consent and until the study completion visit, must be reported to Novartis within 24 hours of learning of its occurrence as described below.

Any SAEs experienced after this period should only be reported to Novartis if the investigator suspects a causal relationship to study treatment.

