#### ***Study Day:***

The study day for safety/efficacy assessments (e.g. adverse event onset, laboratory abnormality occurrence, vital sign measurement, Electrocardiogram (ECG), PK sampling mRS scores, etc.,) will be calculated using the first administration of i.v. dose date as the reference date. For assessments occurring:

**on or after the first administration of i.v. dose date**, the study day will be calculated as (date of assessment/occurrence) – (date of first administration of i.v. dose) + 1. Then study day 1 will be the day of first administration of i.v. dose.

**before the first administration of i.v. dose date**, the study day will be calculated as (date of assessment/occurrence) – (date of first administration of i.v. dose).

For example, if a serious adverse event starts 1 day before the first administration of i.v. dose date, the study day displayed on the listing will be negative, i.e. -1.

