## Commercially Confidential Information

## 8 Statistical methods for safety and tolerability data

The following safety analyses will be performed based on the Safety Set.

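### The SAP 8.2 by-arm AE and SAE tables start at consent, so they credit pre-infusion events to BAF312 or placebo; a first-infusion-to-Day-90 rule is a cheap improvement

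*SAP*

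**What the plan says.** **Collection.** Protocol 9.1 defines an adverse event as an untoward occurrence after written consent "for participation in the study until the end of study visit". Protocol 9.2.2 requires reporting of every SAE in randomized patients "occurring after the patient has provided informed consent and until the study completion visit". Collection therefore begins before dosing.

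**SAP 8.2 tables.** Under Adverse events (AEs), "AEs summarized will be all events recorded during the study". The only onset rule nearby concerns missing dates: "Any AE with a missing start date will be considered as starting in the study". Being in the study is not the same as being after first dose. The list that follows covers AEs and SAEs by system organ class and preferred term (SOC/PT), by arm, and adds that "Fatal SAEs regardless of study drug relationship will be provided by SOC and PT". A patient with several events in one body system counts once towards that system.

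**Population.** SAP section 8 says "The following safety analyses will be performed based on the Safety Set". That set holds dosed patients only (SAP 4.1). It restricts patients, not event onset.

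**Pre-dose events are foreseen.** The Study Day example in SAP 4.4 covers what happens "if a serious adverse event starts 1 day before the first administration of i.v. dose date": such an event is listed with a day below zero.

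**Tables that start at first dose.** SAP 5.2.3 summarizes any treatment-emergent AE (TEAE) and serious TEAE by arm, overall and by severity, with 95% Clopper-Pearson intervals. The window runs from the first injection date to the last injection or intake date. SAP 8.2 also plans two registry tables by SOC/PT: non-serious TEAEs above 1% incidence, and serious TEAEs or SAEs suspected to be related. SAP 5.2.1 sets the safety endpoint period at 90 days.

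**The concern.** Consent, randomization and first infusion are separate steps in the first hours after a bleed. An event that begins between consent and first infusion cannot have been caused by study drug, yet the SAP 8.2 tables place it in the column of the arm the patient later receives. It adds the same expected background to both arms and pulls the ratio of the two percentages towards 1. It also uses up the patient's single count in that body system, so a later event there adds nothing to the total. In the overall summary, events with the same SOC and PT no more than one day apart are merged into one occurrence, so a pre-infusion event and an early recurrence become one.

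Safety is one of the two secondary objectives, and with about 33 patients per arm a single patient is visible in a percentage. The SAP 8.2 tables are also the nearest the plan has to a by-arm, SOC/PT account of events over the full follow-up, so their starting point should be right.

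**Working it through.** The documents give no AE rate, no pre-dose rate and no power for safety, so there is no planned figure to reproduce. The check compares the table definitions and then illustrates the size under stated assumptions.

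**1. Which table covers which period**

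| Table | Starts | Ends | All events by SOC/PT? |
|---|---|---|---|
| SAP 8.2 AE and SAE tables | consent | end of study, about Day 90 | yes |
| SAP 5.2.3 TEAE and serious TEAE summary | first dose date | last dose | no SOC/PT breakdown named |
| Registry, non-serious TEAEs | first dose date | last dose | non-serious only |
| Registry, serious TEAEs or related SAEs | first dose date for TEAEs | last dose for TEAEs; no end stated for related SAEs | serious only |

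Last dose is about Day 14, or about Day 7 for patients who fail the swallowing evaluation. The TEAE window thus covers 14/90 = 15.6% or 7/90 = 7.8% of follow-up and leaves out about 76 to 83 days. No row gives all events by SOC/PT from first dose to Day 90.

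**2. Length of the pre-dose window**

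Protocol 3.1 limits screening/baseline to 24 hours from onset of the bleed, and the consent-to-infusion part is shorter. As a share of observed time, 24 hours is 1/(90 + 1) = 1.1%; 6 hours is 0.25/90.25 = 0.3%.

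**3. Size of the distortion**

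Assumptions, none from the documents: post-dose rates of 20% (BAF312) and 10% (placebo) for some event category; the same pre-dose probability q in both arms; pre-dose and post-dose events independent within a patient; 33 patients per arm (SAP 1.4 gives approximately 33).

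Counted rate = 1 − (1 − q)(1 − p).

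| q | BAF312 | Placebo | Relative risk | Difference, points |
|---|---|---|---|---|
| 0% | 20.0% | 10.0% | 2.00 | 10.0 |
| 1% | 1 − 0.99 × 0.80 = 20.8% | 1 − 0.99 × 0.90 = 10.9% | 1.91 | 9.9 |
| 2% | 1 − 0.98 × 0.80 = 21.6% | 1 − 0.98 × 0.90 = 11.8% | 1.83 | 9.8 |
| 5% | 1 − 0.95 × 0.80 = 24.0% | 1 − 0.95 × 0.90 = 14.5% | 1.66 | 9.5 |

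The difference equals (1 − q)(p₁ − p₀), so it shrinks only by the factor 1 − q. That shrinkage is the masking effect: patients who have both a pre-dose and a post-dose event count once.

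Extra placebo patients counted: 33 × (0.109 − 0.100) = 0.3 at q = 1%, and 33 × (0.145 − 0.100) = 1.5 at q = 5%. One patient moves an arm's rate by 1/33 = 3.0 points.

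**The case against.** The strongest reply is that the plan already protects the safety endpoint. SAP 5.2.3 ties the secondary safety endpoints to treatment-emergent events, by arm and with confidence intervals, and the registry tables add SOC/PT detail for serious and non-serious TEAEs. With 33 per arm, the 1% threshold removes essentially nothing. The SAP 8.2 tables complement these and agree with Protocol 11.5.2, which tabulates adverse events with no treatment-emergent limit. Nothing is tested (SAP 5.2.2 and 5.2.3), and these tables report counts and percentages. The visible SAP mentions relative risk once, for a TEAE graph.

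Much of this stands. A reader might infer that every by-arm safety table is contaminated, or that the 5.2.3 summary alone starts at first dose. The documents support neither. A reader might also infer that the fatal-event table collects deaths before treatment. It cannot, because the Safety Set holds dosed patients only; it can take in only an event that began before dosing and proved fatal afterwards. Tables of related events, discontinuations and dose interruptions can hardly contain events that were over before dosing.

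Other provisions shrink the pool further. Findings before consent go to medical history, and screen failures enter no analysis (SAP 8.2). Listings already show a negative study day for onset on an earlier date.

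What the reply does not answer is the gap between the two sets of tables: one starts too early for a post-dose comparison, and the other mostly stops at last dose.

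**Conclusion.** The point holds as a modest one. By their stated rule, the SAP 8.2 AE and SAE tables include pre-infusion onsets in patients who are later dosed, and no planned SOC/PT table of all events visible in the SAP covers first dose to Day 90.

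The size is small. At an assumed 1% to 5% pre-dose rate, a true relative risk of 2.00 would be tabulated as 1.91 to 1.66, and a 10.0-point difference as 9.9 to 9.5. A reader who assumed pre-dose rates of 10% or 15% would get 1.47 or 1.36 from the same formula (0.280/0.190 and 0.320/0.235). Rates that high for a single category look implausible in a window of under 24 hours, and even at 15% the difference is still 8.5 points. The documents give no pre-dose rate, so every figure depends on the assumed one. No test result changes, and the text does not support a claim that the safety comparison as a whole is compromised.

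**What to change.** In SAP 8.2, state that the by-arm AE and SAE tables include events starting or worsening on or after first infusion through the Day 90 visit, and that events with onset between consent and first infusion are listed separately.

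Two limits should be written in:

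- Do not import the SAP 5.2.3 treatment-emergent definition into these tables. It would remove the follow-up period, which is the larger loss.
- Keep the summary under Deaths complete, with no onset restriction.

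The cost is one sentence and one programming flag before database lock. No information is lost, because pre-infusion events stay in a listing.

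The gain is limited by the data. Protocol 9.1 asks for AE start and end dates and does not mention a start time. Where an event falls on the first-dose date and neither a time nor a before/after-infusion indicator is available, count it as post-dose, which is the conservative choice. The rule then removes only events dated before first dose or timed before it. Removing the rest would need an onset time or a before/after-infusion field for that day.
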